2.1.2 F901318 has potential to address that unmet need

F901318, also known as 2-(1, 5-dimethyl-3-phenyl-1H-pyrrol-2-yl)-N-{4-[4-(5-fluoropyrimidin-2-yl) piperazin-1-yl]-phenyl}-2-oxo-acetamide, is the first of a new class of antifungal agents. F901318 has a novel, well defined mechanism of action, inhibiting a rate limiting enzyme of fungal pyrimidine biosynthesis, DHODH. F901318 potently inhibits fungal DHODH but is a very poor inhibitor of the human enzyme. This differential activity is consistent with the differences in structure between the human and fungal DHODH enzymes.

As discussed in the Nonclinical Pharmacology section of the IB, F901318 is active against a wide range of *Aspergillus* species including those most commonly associated with human infection. Importantly, F901318 is effective against isolates of *A. fumigatus* resistant to other antifungal agents, *Scedosporium* spp. and *Lomentospora prolificans*; the latter is frequently refractory to all available antifungal agents. F901318 is also active against a range of other

filamentous fungi with the notable exception of the zygomycetes. F901318 has no activity against yeasts, zygomycetes, and some *Fusarium* species.

Within F901318's spectrum of activity is an evolving panel of other "uncommon" moulds which are typically resistant to the azole antifungals and/or polyenes, including *Rasamsonia* species as well as *Acremonium*, *Scopulariopsis*, *Microascus*, and *Paecilomyces* species. Treatment with F901318 may be of benefit in these IFDs, particularly in patients unable to tolerate alternative treatment options.

Sustained exposure to F901318 is lethal to fungi. Vacuolation, cell wall thinning, and cell wall rupture are seen. Loss of cell membrane integrity can be shown by viable dye exclusion studies.

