Patients will be treated until they reach a defined treatment endpoint. All patients should receive treatment for at least 14 days. Patients who are considered by the Investigator to have experienced a successful overall outcome will continue treatment with F901318 for at least 7 days after resolution of all clinical signs and symptoms. The maximum duration of treatment in the main study phase will be 90 days. Patients judged to be a success on Days 78-83 (and hence requiring 85-90 days of total treatment) are eligible to receive up to 90 days of treatment in the main study phase (90 days is the maximum duration of nonclinical safety toxicology studies). In addition, at the Investigator's request and after discussion with the Medical Monitor (MM), open-label treatment with F901318 may be continued beyond Day 90 in patients who are considered likely to continue to benefit from ET. The Investigator's request to extend treatment with F901318 must be approved by the MM. In the case of patients proceeding to the ET phase, the end of treatment (EOT) and end of study (EOS) are taken as the day therapy is completed in the main study phase. Extended treatment may continue as required, but will stop if the study drug becomes commercially available or if development of the study drug is terminated for any reason.

If, at any point during the study period, cultures yield F901318-resistant isolates, patients may remain in the study in the presence of clinical improvement, otherwise they will be considered as treatment failures, treatment with F901318 will be stopped, and the patient will be withdrawn from the study.

To assess efficacy and disease progression during treatment the diagnostic test used to enrol the patient will be repeated. It is essential that the same test is used throughout the study, to provide a robust assessment of change. [REDACTED]

Assessment of efficacy at other study visits will be in accordance with local practice and as clinically indicated. In patients with IA, GM testing will be conducted more frequently.

Visits and assessments are scheduled as shown in Table 1 for visits up to Day 84/Day 90 and the post-treatment FU in the main study phase, and in Table 3 for ET visits and the post-ET FU in the extended treatment phase.

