- a) *Lomentospora (Scedosporium) prolificans* (LoPro),
- b) *Scedosporium* spp.,
- c) *Aspergillus* spp.,
- d) Other F901318-susceptible fungi (as described in the IB or based on information provided by the MM, and in either case requiring approval of the MM),

OR

- e) Probable LRTD IA based on EORTC/MSG criteria (Appendix 2) but not meeting the criteria for culture proven invasive fungal infection.

*Enrolment is based on presumed F901318 susceptibility for categories a-c and selected other species as described in the IB. For IFD due to isolates from species of uncertain susceptibility, enrolment may occur with the approval of the MM before isolate susceptibility is confirmed. If an isolate is not available for shipping to the appropriate central lab for susceptibility testing, susceptibility will be predicted from species identification determined locally. If the isolate is subsequently found to be resistant, study therapy may be continued or discontinued based on clinical response at the discretion of the Investigator. Patients with infections due to multiple fungi can be enrolled provided at least one fungus is known or predicted to be F901318-susceptible AND the patient has limited alternative treatment options for that fungus as defined in Inclusion Criterion 7. As a specific example, a patient with simultaneous IA due to an azole-resistant strain and also invasive mucormycosis could be enrolled and treated with the combination of F901318 and isavuconazole. The choice of additional agents to treat other fungi should also consider the limitations applied to allowed medications (Section 5.9.2). Cases of polyfungal infection should be discussed with the MM.

7. Patients will also have limited alternative treatment options based on meeting one or more of the following criteria:

- a) **Known or predicted resistance of the infecting isolate to all licensed agents.** LoPro automatically meets this criterion – other fungi may qualify after discussion with the MM,
- b) **Failure of available therapy.** Failure to improve based on clinical or radiologic grounds despite receiving ≥ 7 days of standard antifungal treatment AND alternative licensed agents are either predicted to be ineffective or are contraindicated,
- c) **Intolerance to available therapy.** Current therapy cannot be continued due to therapy-related adverse reactions (e.g., increase in serum creatinine above upper limit of normal

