2. Known history of allergy, hypersensitivity, or any serious reaction to any component of the study drug.
3. Patients with chronic aspergillosis, aspergilloma or allergic bronchopulmonary aspergillosis.
4. Suspected zygomycosis (mucormycosis) as the IFD used to qualify for the study. Evidence for the presence of F901318 non-susceptible filamentous fungi such as Mucorales should be urgently followed up. Increased vigilance for the possibility of zygomycosis is required for suspected IA with negative baseline GM.
5. Microbiological findings (e.g., virological) or other potential conditions that are temporally related and suggest a different aetiology for the clinical features.
6. HIV infection but not currently receiving antiretroviral therapy. In cases where HIV infection is first diagnosed at the same time as the invasive fungal infection, if antiretroviral therapy is commenced at the time of enrolment, then such patients are eligible for enrolment.
7. Any known or suspected condition of the patient that may jeopardize adherence to the protocol requirements or impede the accurate measurement of efficacy (e.g. neutropenia not expected to resolve, patients with uncontrolled malignancy who are treatment refractory and receiving only palliative therapy).
8. Patients with a concomitant medical condition that, in the opinion of the Investigator, may be an unacceptable additional risk to the patient should he / she participate in the study.
9. Patients previously enrolled in a study with F901318.
10. Treatment with any investigational drug in any clinical trial within the 30 days prior to the first administration of study drug except for unblinded protocols (e.g. open-label oncological regimen variations or biologic studies). *Prior to enrolling patients that are on other open-label studies it is the site's responsibility to ensure that the study criteria for that study allow for enrolment into this study.*
11. Patients receiving treatment limited to supportive care due to predicted short survival time.
12. Unless approved by the MM, patients with a baseline prolongation of QTcF ≥ 500 msec, or at high risk for QT/QTc prolongation, e.g.
 - a) A family history of long QT syndrome
 - b) Other known pro-arrhythmic conditions
 - c) Risk factors for Torsade de Pointes (e.g. uncompensated heart failure, abnormal plasma potassium or magnesium levels that cannot be corrected, an unstable cardiac condition during the last 30 days).

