4.3.4 Patient Withdrawal

All patients are free to withdraw from participation in the study at any time, for any reason, specified or unspecified, and without prejudice to further treatment. The criteria for enrolment are to be followed explicitly. If a patient who does not meet enrolment criteria is inadvertently enrolled, that patient should be withdrawn from the study and the Sponsor or Sponsor's designee must be contacted. An exception may be granted in rare circumstances where there is a compelling safety reason to allow the patient to continue. In these rare cases, the Investigator must obtain documented approval from the Sponsor or Sponsor's designee to allow the patient to continue in the study.

In addition, patients will be withdrawn from study drug and from the study in the following circumstances:

- The Investigator decides that the patient should be withdrawn.
- Intolerable AE; the study drug is to be discontinued and appropriate measures are to be taken. The Sponsor or Sponsor designee must be notified immediately.

- Clinically significant laboratory value; depending on the observed value, the study drug may need to be discontinued. Prompt consultation with the MM is required.
- ALT or AST meet criteria for major enzyme elevation AND total bilirubin $> 1.5x$ ULN (if baseline $< ULN$) OR $> 1.5x$ baseline (if baseline $> ULN$) without evidence of obstruction, malignancy, impaired glucuronidation capacity or another explanation as detailed in Appendix 3. Study drug must be stopped, and patient follow-up must be conducted in accordance with Appendix 3.
- The patient is unwilling to continue in the study (withdrawal of consent).
- Lack of efficacy.
- Lack of compliance with protocol.
- The Sponsor, for any reason, terminates or suspends the study (see also Section 4.3.5).
- Cultures performed during the treatment period yield F901318-resistant isolates judged clinically relevant and there is no clinical improvement in the opinion of the Investigator (considered as treatment failure).

Patients who discontinue the study early will have early termination procedures performed in accordance with the main study phase EOT visit as shown in the Schedule of Events.

Patients who are withdrawn from the study will not be replaced.

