6.3.1 Investigator's Assessment of Overall Response

Diagnostic assessments used to support the Investigators assessment of response include mycological culture, histology/cytology, GM, PCR, other mycology assessments, bronchoscopy and radiology tests used to confirm enrolment of the patient. It is essential, where possible, that the same methods are used for both diagnosis and assessment of overall response. Any additional assessments performed during the course of the study to assess the patients status may also be used to support efficacy response assessments.

The Investigator's assessment of response will be recorded at Day 7, Day 14, Day 28, Day 42, Day 84/EOT main study phase and 4 weeks after EOT in the main study phase. The Investigator will provide his/her opinion of the patient's response, based on the efficacy criteria as described in Section 6.3.1.1 (clinical), Section 6.3.1.2 (radiological), Section 6.3.1.3 (bronchoscopic), Section 6.3.1.4 (mycological) and Section 6.3.1.5 (overall response).

For patients who receive ET with F901318, the Investigator's assessment of overall response will be recorded at each visit to support continued treatment.

If multiple fungal mould pathogens are present, the DRC will separately analyse outcome for each relevant pathogen. Pathogens which were known at baseline to be F901318-resistant and for which alternative concomitant therapy was provided are not separately scored by the DRC. For example, a patient treated with F901318 and isavuconazole for simultaneous azole-resistant aspergillosis and mucormycosis would receive an overall score only for the response of the aspergillosis. As appropriate, the Investigator may provide per-fungus comments on the clinical, radiological, and mycological elements but per-fungus scores for each of these sub-elements are not required.

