6.4.1 Adverse Events

The Investigator is responsible for recording all AEs observed during the study period (main study phase and ET phase) including 4-week post-treatment follow-up.

Definition of an Adverse Event

An AE is defined as any untoward medical occurrence in a patient during the study; the event does not necessarily have a causal relationship with the treatment. This includes any newly occurring event or worsening of a preexisting condition (e.g., increase in its severity or frequency). An AE can therefore be any unfavorable and unintended sign (including an abnormal laboratory finding), symptom, or disease (new or exacerbated) temporally associated with the use of study treatment. Lack of efficacy or insufficient clinical response should not be recorded as an AE.

Events which meet the definition of an AE include:

- Any abnormal laboratory test results (hematology, clinical chemistry, or urinalysis) or other safety assessments (eg, ECG, radiological scans, vital signs measurements), including those that worsen from baseline, considered clinically significant in the medical and scientific judgment of the Investigator (ie, not related to progression of underlying disease).
- Exacerbation of a chronic or intermittent pre-existing condition including either an increase in frequency and/or intensity of the condition.
- New conditions detected or diagnosed after study treatment administration even though it may have been present before the start of the study.
- Signs, symptoms, or the clinical sequelae of a suspected drug-drug interaction.
- Signs, symptoms, or the clinical sequelae of a suspected overdose of either study treatment or a concomitant medication. Overdose per se will not be reported as an AE/SAE unless it is an intentional overdose taken with possible suicidal/self-harming intent. Such overdoses should be reported regardless of sequelae.

Events which **do not** meet the definition of an AE include:

- Any clinically significant abnormal laboratory findings or other abnormal safety assessments which are associated with the underlying disease, unless judged by the Investigator to be more severe than expected for the patient's condition. **Changes in laboratory findings that fulfil the definition of an AESI must ALWAYS be reported as an AESI (AND as an SAE if any seriousness criteria are also met).**

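### Section 4.1's stopping rule for F901318-resistant isolates is wider than the one in 4.3.4, and neither exempts a known resistant co-pathogen treated with another agent

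*Protocol*

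**What the plan says.** Two sections of the protocol mandate withdrawal for a resistant isolate.

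- **Section 4.1** applies if, "at any point during the study period, cultures yield F901318-resistant isolates". The only escape is clinical improvement; "otherwise they will be considered as treatment failures, treatment with F901318 will be stopped, and the patient will be withdrawn from the study".
- **Section 4.3.4** withdraws the patient from drug and study on this condition: "Cultures performed during the treatment period yield F901318-resistant isolates judged clinically relevant and there is no clinical improvement in the opinion of the Investigator".

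The protocol also expects some patients to carry fungi that F901318 does not cover.

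- Section 2.1.2 states that "F901318 has no activity against yeasts, zygomycetes" and some *Fusarium* species.
- Inclusion Criterion 6 (Section 4.3.1) requires only one susceptible fungus, and its own example is that "a patient with simultaneous IA due to an azole-resistant strain and also invasive mucormycosis could be enrolled".
- Exclusion Criterion 4 (Section 4.3.2) bars "Suspected zygomycosis (mucormycosis) as the IFD used to qualify for the study", so mucormycosis as a second infection is not excluded.
- Section 6.3.1 says: "Pathogens which were known at baseline to be F901318-resistant and for which alternative concomitant therapy was provided are not separately scored by the DRC". The example it gives is again aspergillosis with mucormycosis.

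Section 5.1 requires at least 14 days of treatment unless one of the 4.3.4 withdrawal criteria applies.

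**The concern.** Both rules are mandatory, but their triggers differ. Section 4.1 has no test of clinical relevance, so a stable patient with an incidental resistant isolate must be stopped under 4.1 and need not be under the 4.3.4 resistance criterion. Centres that read different sections could handle the same patient differently.

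Beyond that mismatch, both sections are silent on the co-pathogen that the protocol knowingly admits. A patient with aspergillosis and mucormycosis who has not yet improved could lose F901318 because of an organism the drug was never meant to treat, and which the DRC does not score separately.

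These patients were enrolled because they have few alternatives. The study is single-arm, so no concurrent control arm would share the effect of uneven handling.

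**Working it through.** No figure in the plan needs to be reproduced. The check sets the texts side by side and then follows an affected patient into the Day 42 analyses.

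**Which rule catches whom** (isolate cultured on treatment)

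| Patient | Section 4.1 | Section 4.3.4 resistance criterion |
|---|---|---|
| Improving, any resistant isolate | May stay | Not met |
| Stable, incidental isolate | Stop and withdraw | Not met |
| Not yet improved, treated Mucorales co-pathogen known at baseline, judged clinically relevant | Stop and withdraw | Stop and withdraw |
| Same patient, isolate judged not clinically relevant | Stop and withdraw | Not met |

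Rows 2 and 4 show the mismatch between the sections. Row 3 shows that bringing the 4.3.4 limits into 4.1 would not protect the co-pathogen patient.

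**Inputs for the endpoint**

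- Primary classification (SAP 16.1.1): Failure-Stable, Failure-Progression, death, and missing or non-evaluable Day 42 data are all failures.
- Stable-as-success classification (SAP 16.1.1): Failure-Stable moves to success; missing or non-evaluable data remain failures.
- Patients withdrawn from drug are not asked back for Day 42 (Protocol Table 1, footnote b).
- Those withdrawn for an unsuccessful outcome are failures at all later timepoints (Protocol 8.2.2; SAP 16.1.1, under the primary classification).
- N: 100 at the initial CSR and about 200 in total. I take the mITT set to be of that size; a smaller set makes each patient weigh slightly more.

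**Effect of stopping one patient before Day 42 instead of keeping the patient on drug**

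1. Primary rate, patient would have stayed stable: failure if kept, failure if stopped. Change = 0.
2. Primary rate, patient would have improved to Success-Partial or better by Day 42: success if kept, failure if stopped. Change = 1/N, which is 1/100 = 1.0 point or 1/200 = 0.5 point.
3. Stable-as-success rate, patient would have stayed stable: success if kept. If stopped, the patient becomes a failure mainly because Day 42 data are missing or non-evaluable. Change = 1/N, again 1.0 or 0.5 point.

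Step 3 does not apply if Table A would class the kept patient as Failure-Progression, because alternative systemic antifungal treatment is required or a recurrent or emergent infection is documented. That patient fails either way.

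The documents give no number of affected patients. If one assumes 1 to 5, the stable-as-success rate moves by 1/100 to 5/100 = 1.0 to 5.0 points at N = 100, and by 1/200 to 5/200 = 0.5 to 2.5 points at N = 200.

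**The case against.** The strongest reply is that 4.1 is a design summary and 4.3.4 is the operative withdrawal section. Section 5.1 supports this by naming 4.3.4 when it says which criteria may cut treatment short. That stands as a pointer and lowers the risk in practice, but it is not a precedence clause, and 4.1 is written as an instruction.

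Several stronger readings are tempting, and the documents do not support them.

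- **That 4.3.4 already protects the known co-pathogen.** It does not: it has no such exception, and a Mucorales isolate can readily be judged clinically relevant.
- **That 4.1 is materially wider in time.** Section 6.4.1 does use the term broadly, "during the study period (main study phase and ET phase) including 4-week post-treatment follow-up". But in post-treatment follow-up there is no drug to stop, and in extended treatment the patient is still being treated.
- **That leaving out the Investigator's opinion matters.** Clinical response is assessed by the Investigator throughout conduct, and 4.1 names no other assessor.
- **That any Candida culture forces withdrawal.** Section 5.9.2.1 allows fluconazole for candidiasis at any time, and Section 6.3.1.4 does not require yeast material to be shipped. The protocol's scheme is plainly not to treat yeasts this way.
- **That 4.1 overrides the discretion in Inclusion Criterion 6 when an enrolling isolate proves resistant.** The tension exists only for a patient who is not improving, and 4.3.4 would also withdraw that patient if the isolate is clinically relevant.

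Two further safeguards count for the plan. Polyfungal cases should be discussed with the Medical Monitor, and 4.3.4 lets the Investigator withdraw a patient on other grounds, such as lack of efficacy, whatever 4.1 says.

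What remains is the missing relevance test in 4.1 and the missing co-pathogen exception in both sections.

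**Conclusion.** The point holds and is minor. Section 4.1 omits the clinical-relevance limit in 4.3.4, and neither section exempts a resistant co-pathogen known at baseline and treated with another agent. Followed as written, 4.1 could remove eligible patients with few alternatives. Section 4.3.4 could do the same to the co-pathogen patient if the isolate is judged clinically relevant.

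A reader might infer that the primary result is at risk. For a patient who stays stable it is not: the change is 0. It could change by 1.0 point (N = 100) or 0.5 point (N = 200) for each patient who is stopped early and would have improved by Day 42. The stable-as-success rate could change by the same amount for each stable patient stopped before Day 42.

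These sizes rest on an mITT set of 100 or 200. The 1 to 5 affected patients are an assumption, so no total effect can be claimed.

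**What to change.** Make two edits, so that the sections agree.

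1. In Section 4.1, replace the sentence with a cross-reference to the 4.3.4 resistance criterion, in the same terms: culture on treatment, isolate judged clinically relevant, no improvement in the Investigator's view.
2. In Section 4.3.4 itself, add text such as:

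> This criterion applies to the qualifying pathogen(s) treated with F901318 and to clinically relevant new resistant moulds. It does not apply to F901318-resistant co-pathogens known at baseline and treated with other agents, or to yeasts managed under Section 5.9.2.1. For an enrolling isolate found resistant after enrolment, Inclusion Criterion 6 applies.

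The exceptions must go in 4.3.4. Placed only in 4.1, they would leave 4.3.4 still mandating withdrawal of the patients 4.1 had exempted.

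The cost is a few sentences in 4.1 and 4.3.4 at the next amendment, with no new data. The SAP needs no edit: Table A already covers patients who need alternative systemic antifungal treatment or have a recurrent or emergent infection, and the rest stay with DRC adjudication.
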